7.1. Scale and Duration

The Vortex Feasibility Study will be conducted at up to 3 centers in Australia and Europe with planned enrollment up to 10 subjects. All subjects will be screened according to the protocol inclusion and exclusion criteria. Follow-up will occur through 72 hours or hospital discharge, whichever comes first. The study design is summarized below in **Figure 7.1-1**.

* Subjects who provide informed consent are considered enrolled as soon as an attempt is made to insert any part of the Vortex System into the subject’s femoral artery.

‡ ≤72 hours or discharge, whichever comes first

Figure 7.1-1: Vortex Feasibility Study Design Overview

7.2. Treatment Assignment

7.3. Subjects who are candidates for high-risk percutaneous coronary intervention, provide written informed consent, and are eligible to be treated with the Vortex System will be evaluated for enrollment in this study. Prior to being eligible for

the study, a subject must meet all of the inclusion criteria (Section 8.2) and none of the exclusion criteria (Section 8.3). Justification for the Study Design

In order to provide an assessment of safety and performance of the Vortex System while also limiting the potential exposure of study subjects to risk, the sample size in this feasibility study has been limited to up to 10 subjects at up to 3 investigative centers in Australia and Europe. Technical Success, Clinical Success, and safety results will be reported on all enrolled subjects through 72 hours or hospital discharge, whichever comes first.

8. Subject Selection

8.1. Study Population and Eligibility

Subjects who are candidates for high-risk percutaneous coronary intervention, provide written informed consent, and are eligible to be treated with the Vortex System will be evaluated for enrollment in this study. Prior to being eligible for the study, a subject must meet all of the inclusion criteria (Section 8) and none of the exclusion criteria (Section 8.2).

8.2. Inclusion Criteria

Subjects who meet all of the following criteria (see **Table 8.2-1**) may be given consideration for inclusion in this clinical investigation, provided no exclusion criterion (see Section 8.2) is met.

Table 8.2-1: Inclusion Criteria

IC1. Subject provides signed informed consent.
 
IC2. Subject is ≥ 18 years and < 90 years of age.
 
IC3. Subject is indicated for NON-emergent PCI of at least one de novo or restenotic lesion in a native coronary vessel or coronary artery bypass graft and has left ventricular ejection fraction (LVEF) $\leq 50\%$ with the following:
 
 • Unprotected left main -OR- • Last remaining vessel -OR- • Three vessel disease ($\geq 50\%$ diameter stenoses by visual estimate or total occlusion)

Abbreviations: LVEF=left ventricular ejection fraction; PCI=percutaneous coronary intervention

8.3. Exclusion Criteria

Subjects who meet any one of the following criteria (**Table 8.3-1**) cannot be included in this study or will be excluded from this clinical study.

Table 8.3-1: Exclusion Criteria

- EC1. Subject has had STEMI within 24 hours.
- EC2. Subject has had pre-procedure cardiac arrest requiring CPR within 24 hours of enrollment.
- EC3. Subject is in shock, defined as follows:
- CI < 2.2 L/min/m² and PCWP > 15 mmHg -AND-
 - Hypotension (systolic blood pressure < 90 mmHg for > 30 minutes) -OR-
 - Need for supportive measures (i.e., inotropes or mechanical support) to maintain systolic blood pressure ≥ 90 mmHg and end organ hypoperfusion (cool extremities or urine < 30 mL/hour and a heart rate > 60 beats per minute)
- EC4. Subject has left ventricular mural thrombus.
- EC5. Subject has a prosthetic aortic valve.
- EC6. Subject has pericarditis or constrictive heart disease (constrictive pericarditis or restrictive cardiomyopathy).
- EC7. Subject has moderate or greater aortic valve stenosis³¹ or moderate or greater aortic valve insufficiency³¹ (by echocardiographic assessment, graded as ≥ 2+).
- EC8. Subject has abnormalities of the aorta that preclude safe delivery of the device, including severe calcification, tortuosity, aneurysm, or prior surgery.
- EC9. Subject has PVD preventing passage of the device (e.g., calcification, small caliber) or tortuosity that would preclude safe placement of the 16 Fr introducer sheath.
Note: Minimum required vessel diameter is > 5.5 mm.
- EC10. Subject has advanced renal dysfunction (AKIN^{29,30} Stage 3).
- EC11. Subject has a history of liver dysfunction (Childs Class C) with elevation of liver enzymes and bilirubin > 3× ULN or INR ≥ 2.
- EC12. Subject has had a recent (within 1 month) stroke or TIA.
- EC13. Subject has known hypersensitivity to intravenous contrast agents that cannot be adequately pre-medicated or has known hypersensitivity to heparin, aspirin, ADP receptor inhibitors or nitinol.
- EC14. Subject has current or a history of heparin induced thrombocytopenia.
- EC15. Subject has uncorrected abnormal coagulation or platelet count ≤ 75,000/mm³ or INR ≥ 2.0.
- EC16. Subject has significant right heart failure (RAP > 15 mmHg, RVSWI < 0.30 mmHg·L/m², PVR > 3.6 Woods units)³².
- EC17. Subject requires mechanical ventilation.
- EC18. Subject has an atrial or ventricular septal defect (including post-infarct VSD).
- EC19. Subject has left ventricular rupture.
- EC20. Subject has cardiac tamponade.
- EC21. Subject has severe pulmonary disease (FEV1 < 1L).
- EC22. Subject has sustained or non-sustained ventricular tachycardia.
- EC23. Subject is breast feeding or is pregnant.
- EC24. Subject has other disease condition(s) resulting in the subject being unsuitable for participation in the clinical trial (e.g. advanced malignancy with limited expected survival)

Table 8.3-1: Exclusion Criteria

EC25. Subject has other disease condition(s) which the Investigator has determined may cause non-compliance to the study requirements.

Abbreviations: CI=cardiac index; CPR=cardiopulmonary resuscitation; FEV=forced expiratory volume; INR=international normalization ratio; PCWP=pulmonary capillary wedge pressure; PVD=peripheral vessel disease; PVR=pulmonary vascular resistance; RAP=right atrial pressure; RVSWI=right ventricular stroke work index; STEMI=ST-elevation myocardial infarction; TIA=transient ischemic attack; ULN=upper limit of normal; VSD=ventricular septal defect

9. Subject Accountability

9.1. Point of Enrollment

Subjects who provide written informed consent and are confirmed eligible for the study are considered enrolled in the study as soon as an attempt is made to insert any part of the Vortex System into the subject's femoral artery (e.g., Vortex sheath).

9.2. Withdrawal

All subjects enrolled in the clinical study (including those withdrawn from the clinical study) shall be accounted for and documented. If a subject withdraws from the clinical investigation, the reason(s) shall be reported. If such withdrawal is due to problems related to investigational device safety or performance, the investigator shall ask for the subject's permission to follow his/her status/condition outside of the clinical study.

While all efforts should be made to minimize attrition, subjects may withdraw from the study at any time, with or without reason and without prejudice to further treatment. Withdrawn subjects will not undergo any additional study follow-up, nor will they be replaced. The investigator may discontinue a subject from participation in the study if the investigator feels that the subject can no longer fully comply with the requirements of the study or if any of the study procedures are deemed potentially harmful to the subject. Data that have already been collected on withdrawn subjects will be retained and used for analysis, but no new data will be collected after withdrawal. All applicable case report forms up to the point of subject withdrawal and an "End of Study" form for the subject must be completed.

[figure not shown]

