7.3 Methods for Handling Missing Data

All subjects who are enrolled will be eligible for evaluation. Handling of dropouts and missing data will depend on their frequency and the nature of the outcome measure. All data will be included in the analysis unless judged to be invalid.

When calculating rates of adverse events, missing and partial dates will be handled as shown in the table below.

Partial Date	Action Taken
Entire adverse event onset date is missing	The procedure date will be used for the onset date.
The month and the day of the month are missing but the year is available	January 1 st will be used for the month and day of the onset date. However, if the imputed date falls before the procedure date, then the procedure date will be used for the onset date.
Day is missing, but the month and year are available	The 1 st will be used as the day of the onset date. However, if the imputed date falls before the procedure date, then the procedure date will be used for the onset date.

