7.4.3 Denominator using Sufficient Follow-up for Endpoints and Additional Measurements

All subjects in the specific analysis sets (ITT or PP) will be included in the denominator for the analysis for the primary endpoint and additional measurements. All subjects are considered as having sufficient follow-up through 72 hours or hospital discharge, whichever comes first.

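### Study data stop at withdrawal whatever its cause, yet the SAP deems every subject fully followed, so a later event would by default go uncounted

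*Protocol*

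**What the plan says.** **Protocol 9.2 (Withdrawal).** "Withdrawn subjects will not undergo any additional study follow-up, nor will they be replaced". What was gathered before withdrawal is kept and analysed, but "no new data will be collected after withdrawal". The investigator may end a subject's participation for expected non-compliance or if "any of the study procedures are deemed potentially harmful to the subject". Where withdrawal is due to a safety or performance problem with the device, "the investigator shall ask for the subject's permission to follow his/her status/condition outside of the clinical study". Nothing says how that information would enter the study database.

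**Protocol, Table 10.1-1, footnote k, and Section 7.3.** Footnote k has adverse events collected in every subject from enrollment to 72 hours after the procedure or discharge, whichever is earlier. Section 7.3 promises Technical Success, Clinical Success and safety results for everyone enrolled over the same period.

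**SAP 7.4.3.** All ITT or per-protocol subjects are in the denominator for the primary endpoint and the additional measurements. "All subjects are considered as having sufficient follow-up through 72 hours or hospital discharge, whichever comes first". Withdrawal is not mentioned.

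**SAP 7.3.** "Handling of dropouts and missing data will depend on their frequency and the nature of the outcome measure". The only concrete rules there concern missing or partial adverse event onset dates.

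**Endpoint (Protocol 11.1.1, SAP 3.1).** Clinical Success is freedom from conversion to open heart surgery and from death in hospital. It is reported as numerator, denominator and proportion (SAP 3.1.3), as are the safety measures (SAP 3.2.1).

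**The concern.** Clinical Success and each safety rate are determined by whether an adverse outcome was recorded. Such endpoints are only as good as the observation behind them: if observation stops early and the subject is still treated as fully observed, silence is read as a good result.

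Section 9.2 creates that situation inside the defined window. A subject may be discontinued by the investigator, still be an inpatient, not have withdrawn consent, and yet contribute no further data. For a device-related withdrawal, the information most relevant to a first-human-use study is directed away from the dataset. A withdrawal for that reason could plausibly be related to outcome, so the loss need not be neutral.

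At stake are the reported Clinical Success rate and the safety event rates, both of which can err only in the device's favour by this route.

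**Working it through.** The plan has no calculated figure to reproduce. The sample size is an arbitrary maximum of 10 (Protocol 11.1.1.2, SAP 3.1.2), with no hypothesis and no assumed rate. The check therefore has two parts.

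**1. Following one subject through the rules.** Take a subject who is discontinued after the procedure, with no event so far, and who dies in hospital before 72 hours.
- Protocol 9.2: no further study follow-up, so the death is not in the study data.
- Footnote k and Protocol 7.3: the death should have been collected and reported. These cannot both hold alongside 9.2.
- SAP 7.4.3: the subject is in the denominator and is deemed sufficiently followed.
- SAP 3.1: no death or surgery on record, so the subject scores as a Clinical Success unless another rule intervenes.
- SAP 7.3: could intervene, but states no rule for unknown endpoint status.

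For an unseen complication the path is the same, except that it affects only the relevant safety rate, where the subject scores as event-free.

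**2. Size.** One subject moves a proportion by 1/n; at n = 10 that is 10 percentage points. Suppose all other subjects succeed. Exact (Clopper-Pearson) 95% intervals:

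| Withdrawn, status unknown | Counted as success | Excluded | Counted as failure |
|---|---|---|---|
| 1 of 10 | 10/10 = 100% (69.2–100) | 9/9 = 100% (66.4–100) | 9/10 = 90% (55.5–99.7) |
| 2 of 10 | 10/10 = 100% (69.2–100) | 8/8 = 100% (63.1–100) | 8/10 = 80% (44.4–97.5) |

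The middle column is for comparison only, since SAP 7.4.3 does not allow exclusion. For a safety event the mirror image applies: 0/10 = 0% (0–30.8) against 1/10 = 10% (0.3–44.5).

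**How often could it arise?** The documents give no withdrawal rate, so the rates d below are assumptions. The chance of at least one withdrawal among 10 is 1 − (1 − d)^10:
- d = 1%: 9.6%
- d = 5%: 40.1%
- d = 10%: 65.1%
- d = 20%: 89.3%

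With a window of at most 72 hours, the low end is the more credible.

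**Average effect.** If a withdrawn subject has an unseen event with probability q, also an assumption, the mean upward bias in Clinical Success is d × q. With d = 5% and q = 3.4% (the in-hospital mortality that Protocol 4.1.2 cites from a registry of another pump), it is 0.05 × 0.034 = 0.17 percentage points. With d = 10% and q = 50%, it is 5 points. The average effect is small unless withdrawal is strongly tied to outcome; the 10-point figure is what happens if a case occurs.

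**The case against.** Several stronger readings are tempting, and the documents do not support them.

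- *The plan codes withdrawn subjects as successes.* No section says so. SAP 7.4.3 fixes the denominator and SAP 7.3 leaves handling open. Scoring as success is the default result of the stated rules, not a declared rule.
- *Unseen complications become successes.* Clinical Success contains only open heart surgery and in-hospital death. An unseen complication lowers a safety count and leaves the primary endpoint alone.
- *Stopping the pump takes a subject out of the study.* Section 9.2 concerns leaving the study. Pump removal is planned in every case, and the ITT set includes subjects in whom the device was never used.
- *Subjects with device problems are the ones most likely to leave.* Nothing shows this. Support is intended for up to 4 hours (Protocol 5), with the subject sedated (Protocol 10.7.1). A problem would usually appear then and be recorded as a Technical Success failure, a device deficiency or an adverse device effect. Data obtained before withdrawal are retained.

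It can also be said that 9.2 does not expressly equate investigator discontinuation with withdrawal, that reasons for withdrawal must be reported, and that 10 subjects can be read case by case.

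All of this narrows the point, but three gaps remain. Section 9.2 treats investigator discontinuation under the withdrawal heading and does not say that data collection continues. Disposition summaries and subject listings are only optional in the SAP (5.1, 5.6). And a reported reason for leaving does not supply the outcome that followed.

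**Conclusion.** The point holds in limited form. Protocol 9.2 conflicts with footnote k and Section 7.3 on whether outcomes are collected in everyone enrolled. SAP 7.4.3 assumes complete follow-up that 9.2 does not deliver, and SAP 7.3 gives no rule to fill the gap. By default, a death or open heart surgery after withdrawal but within the window would go uncounted and the subject would score as a Clinical Success; an unseen complication would score as event-free.

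Events recorded before withdrawal still count, and Technical Success is usually settled at the procedure. The size is up to 10 percentage points per affected subject at n = 10. That is a ceiling: it assumes the withdrawn subject does have an unrecorded event. A reader might infer an expected bias of 10 or 20 points, but with no stated withdrawal rate and so short a window, no such expectation can be derived. The matter is worth correcting because a single lost death would be a central result in a first-human-use study.

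**What to change.** 1. **Protocol 9.2.** State that a subject discontinued by the investigator who has not withdrawn consent stays in data collection for the primary endpoint and the Section 6.3 events to the end of the defined window. Reconcile 9.2 with footnote k and Section 7.3.
2. **Protocol 9.2 and the consent form.** Ask a subject who withdraws for permission to record vital status, open heart surgery and device-related serious adverse events to the end of that window, and enter these in the study database.
3. **SAP 7.4.3.** Limit the statement on sufficient follow-up to subjects observed to the end of the window or with an event before that.
4. **SAP 7.3.** For these endpoints, replace the frequency-dependent sentence with a prespecified rule. Show Clinical Success and each event rate twice, with unknown-status subjects counted once as failures or events and once as successes or event-free. List each withdrawal with its reason.

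The cost is minor wording in both documents and a small consent-form change. No visits are added and the right to withdraw is untouched. The reported success rate may look less favourable under one of the two counts.

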9.3. End-of-Study Definition

This clinical study will be considered completed when subjects are no longer being examined or the last subject's last study visit as outlined in the data collection schedule (**Table 10.1-1**) has occurred.

10. Study Methods

10.1. *Data Collection*

This section indicates the data needed to fulfill the objectives of this clinical study. Boston Scientific Corporation (BSC) considers data collected from clinical trial subjects to be personal data (see definitions of different data categories in **Table 24.2-1**) and compliance with privacy and data protection laws and regulations (for example, the General Data Protection Regulation [GDPR], see **Table 24.2-1**) to be critically important. Data collection for this clinical study has been carefully considered to comply with data privacy laws. The data collection schedule is shown in **Figure 10.1-1** and **Table 10.1-1**. Additional information on data collection can be found in Sections 10.3 through 10.10.

* Subjects who provide informed consent and are confirmed eligible are considered enrolled in the study as soon as an attempt is made to insert any part of the Vortex System into the subject’s femoral artery.

‡ ≤72 hours or discharge, whichever comes first

¶ Includes AE, SAE, ADE, SADE, USADE, and IMR events

Figure 10.1-1: Vortex Study Data Collection Schedule

See Table 10.1-1 for additional information.

Table 10.1-1: Data Collection Schedule

Assessment	Baseline	Index Procedure	≤72 Hours / Discharge ^a
Signed Informed Consent Form	X	–	–
Demographics and medical history ^b	X	–	–
Physical assessment ^c	X	–	–
New York Heart Association classification	X	–	X
CCS Angina classification	X	–	–
Electrocardiogram ^d	X	–	X
Laboratory tests ^e	X	O	X
Assessment of iliofemoral diameter and tortuosity ^f	X	–	–
Anticoagulant medications	X	X	X
Other cardiovascular medications	X	X	X
Transthoracic echocardiography ^{g,h}	X	X	–
Coronary angiogram ^{h,i}	X	X	–
Intracardiac echocardiography ^h	–	O	–
Activated clotting time	–	X	–
Device deficiencies ^j	–	X	X
Adverse event assessment ^k	–	X	X

Note: X = required; O = optional; – = not required.

Additional information on data collection can be found in Sections 10.3 through **10.10**.

a: Data collected through 72 hours or hospital discharge, whichever comes first.

b: Including cardiac, neurological, renal, and peripheral vascular disease.

c: Including weight, height, and vital signs.

d: 12-lead ECG; baseline ECG should be done within 30 days prior to the index procedure; post-procedure timing is per standard of care for HR-PCI.

e: Laboratory tests at baseline include CBC with platelets, serum creatinine, plasma-free hemoglobin, and cardiac enzymes. Post-procedure, cardiac enzymes (CK or troponin is required, CK-MB or troponin if CK is elevated) must be collected once per standard of care within 6–24 hours; if readings are abnormal, a second collection per standard of care is required. Plasma-free hemoglobin must be collected pre-discharge (≥ 6 hours post procedure). Plasma-free hemoglobin may be collected during the index procedure per the standard of care.

f: Minimum required iliofemoral diameter is > 5.5 mm; any assessment technique to determine diameter and tortuosity is permitted; assessment must be done within 365 days prior to the index procedure.

g: TTE assessment should be done within 180 days prior to the index procedure.

h: Deidentified copies of the imaging assessments should be provided to Boston Scientific.

i: Coronary angiogram should be done within 365 days prior to the index procedure per standard of care for HR-PCI.

j: Information on device deficiencies for the test device will be monitored and reported to Boston Scientific.

k: The adverse event assessment includes AE, SAE, ADE, SADE, USADE, and IMR events, which will be collected from the time of enrollment through 72 hours post-procedure or hospital discharge, whichever comes first, in all subjects. Please refer to Section 18.1 for reportable events, including a list of IMR events, and to **Table 24.2-1** for definitions of these events, which specify data required for IMR adjudication.

Abbreviations: AE=adverse event; ADE=adverse device effect; CBC=complete blood count; CCS=Canadian Cardiovascular Society; CK=creatinine kinase; CK-MB=creatinine kinase myoglobin band; ECG=electrocardiogram; HR-PCI=high risk percutaneous coronary intervention; IMR=independent medical

Table 10.1-1: Data Collection Schedule

Assessment	Baseline	Index Procedure	≤72 Hours / Discharge ^a
------------	----------	-----------------	------------------------------------

reviewer; SADE=serious adverse device effect; SAE=serious adverse event; USADE=unanticipated serious adverse device effect

